 □ Interviews, questionnaires, surveys □ Educational or cognitive tests □ Focus groups ☑ Observation ☑ Non-invasive imaging or testing (MRI, EEG, pulse oximetry, etc.) □ Administration of contrast agent □ Imaging procedures or treatment procedures that involve radiation (x-rays, CT scans, CT-guided biopsies, DEXA scans, MUGA or PET scan) □ Biopsy conducted solely for research purposes □ Use of placebo □ Sham surgical procedure □ Collection of data from wearable tech such as Fitbit, Apple Watch, Garmin, motion actigraphs, etc.) 	

☐ Fitness tests or other exertion activities ☐ Use of mobile health apps or other apps

☐ Social media-based research activities☐ None of the above	
7.9 * PROCEDURES / METHODS: (REQUIRED)	
For clinical research, list all study procedures, tests and treatments required for this study, including when and how often they will be performed. If there are no clinical procedures, describe the research activities.	
If some of the activities would occur even if the person were not in the study, as in the case of treatment or tests performed for diagnostic purposes, clearly differentiate between those activities that will be done solely for research purposes and those that are happening as part of routine care.	
Examples may include:	
 additional scans outside standard clinical diagnosis or monitoring additional biopsies to collect tissue for research extra clinic visits extra lab tests not required for clinical care 	
If you have a procedure table, attach it to the submission with your other study documents.	
Patients will be randomized to intra-vaginal culture (IVC) of embryos using INVOcell or traditional in-vitro fertilization (IVF) of embryos. Both groups of patients will receive the same initial workup, consultation and evaluation, ovarian stimulation, cycle monitoring, oocyte retrieval, and embryo transfer. The only difference between the two groups will be the culturing/growth of the embryos, which will be randomized to IVC or IVF. All embryos will be transferred on day 3. The IVC protocol is attached for reference.	
7.10 STANDARD CLINICAL PRACTICE: To what extent, if any, do the planned research proc from the care that people would otherwise receive at this institution or the study site done locally:	

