The only difference in clinical practice the "cases" from this randomized controlled trial would have that differed from the "control" population, would be the use of intravaginal culture (IVC) using the INVOcell device instead of the standard in-vitro fertilization (IVF) for fertilization and growth of embryos.	
7.12 * BIOSPECIMEN COLLECTION: Are you drawing any blood or collecting other biosamp buccal swabs, urine, saliva, hair, etc.): (REQUIRED)	les (e.g. tissue,
● Yes ○ No	
* Could this study generate genetic data that may be broadly shared (e.g., submitted to NIH in compliance with Genomic Data Sharing (GDS)/Genome-Wide Association Studies (GWAS) requirements): (REQUIRED)	
○ Yes • No	

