Based on current research trends, we strongly recommend including the genomic data sharing language in the consent form to allow future sharing, even if you don't anticipate it now. It's easier than trying to reconsent all the specimen donors! 7.13 * TYPE OF SPECIMENS (check all that apply): (REQUIRED) **▼** Blood Tissue (describe below): Existing/archival materials (name source below): --Other (describe below): Describe and/or name source: Because patients will not be randomized to either arm of the study (IVC versus IVF) until the day of trigger, they will receive the standard of care and workup that all infertility patients receive when they come to UCSF Center for Reproductive Health for their care. No additional blood tests, tissue collection or biopsies will be performed beyond the standard of care. Therefore, all patients will have their blood drawn for evaluation of the etiology of their infertility, possible tracking hormone levels during their stimulation cycle, and have embryo transfers performed. 7.14 * SPECIMENS ARE: (check all that apply): (REQUIRED) Leftover specimens from a clinical diagnostic or therapeutic procedure Specimens collected for research purposes only (including extra samples taken during a clinical procedure) ✓ Other Explain **Other**: Specimens collected will be the same that are all part of standard care for patients under infertility evaluation. These include: blood samples and embryos (that will belong to patient and be transferred to uterus or frozen for later use by patient). 7.15 * DESTINATION: Specimens will ultimately be stored (check all that apply): (REQUIRED) Outside Entity: Cooperative group bank □ NIH ☐ Other university Industry sponsor Other UCSF: UCSF repository/bank being established under this protocol Existing UCSF specimen repository/bank with CHR approval Other location at UCSF (please describe) Provide the name of the bank and iRIS approval number (if not being

University of California San Francisco - Center for Reproductive Health - Embryology Lab

the location or lab:

banked at UCSF under this protocol). If you checked 'Other,' please provide

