number of mature oocytes retrieved. This comparison will take place on day-3, as that is when the IVC embryos will be assessed. b. Embryo quality. This is measured by the Gardner grading system. c. Implantation rate, which is defined by number gestational sacs seen on early pregnancy 6-week ultrasound divided by number of embryos transferred d. Clinical pregnancy rate, which is defined by the number of fetal poles with heartbeat seen on ultrasound divided by the number of embryos transferred e. Live birth rate, which is defined by the number of living babies delivered divided by the number of transfers To determine the effect of IVC with INVOcell device versus conventional IVF while using oral stimulation or minimal gonadotropins stimulation protocols on: a. Live birth rate, which is defined by the number of live births divided by the number of transfers 7.26 REFERENCES: List only the 5-10 most relevant references (a separate bibliography can be attached for reference purposes if this study involves novel approaches, agents, or an emerging technology		
 c. Implantation rate, which is defined by number gestational sacs seen on early pregnancy 6-week ultrasound divided by number of embryos transferred d. Clinical pregnancy rate, which is defined by the number of fetal poles with heartbeat seen on ultrasound divided by the number of embryos transferred e. Live birth rate, which is defined by the number of living babies delivered divided by the number of transfers To determine the effect of IVC with INVOcell device versus conventional IVF while using oral stimulation or minimal gonadotropins stimulation protocols on: a. Live birth rate, which is defined by the number of live births divided by the number of transfers 7.26 REFERENCES: List only the 5-10 most relevant references (a separate bibliography can be attached for reference purposes if this study involves novel approaches, agents, or an emerging technology 	number of mature oocytes retrieved. This comparison will take place on day-3, as that is	

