 d. Clinical pregnancy rate, which is defined by the number of fetal poles with heartbeat seen on ultrasound divided by the number of embryos transferred e. Live birth rate, which is defined by the number of living babies delivered divided by the number of transfers To determine the effect of IVC with INVOcell device versus conventional IVF while using oral stimulation or minimal gonadotropins stimulation protocols on: a. Live birth rate, which is defined by the number of live births divided by the number of transfers 7.26 REFERENCES: List only the 5-10 most relevant references (a separate bibliography can be attached for reference purposes if this study involves novel approaches, agents, or an emerging technology 	c. Implantation rate, which is defined by number gestational sacs seen on early pregnancy 6-	
 a. Live birth rate, which is defined by the number of live births divided by the number of transfers 7.26 REFERENCES: List only the 5-10 most relevant references (a separate bibliography can be attached for reference purposes if this study involves novel approaches, agents, or an emerging technology 	d. Clinical pregnancy rate, which is defined by the number of fetal poles with heartbeat seen on ultrasound divided by the number of embryos transferrede. Live birth rate, which is defined by the number of living babies delivered divided by the	
 7.26 REFERENCES: List only the 5-10 most relevant references (a separate bibliography can be attached for reference purposes if this study involves novel approaches, agents, or an emerging technology 		
for reference purposes if this study involves novel approaches, agents, or an emerging technology		
	for reference purposes if this study involves novel approaches, agents, or an emergin	

- 1. Mascarehas, M.N., et al., *National, Regional, and Global Trends in Infertility Prevalence Since 1990: A Systematic Analysis of 277 Health Surveys.* PLOS Medicine, 2012. 9(12): p. e1001356.
- 2. Unisa, S., *Childlessness in Andhra Pradesh, India: Treatment-seeking and consequences.* Reproductive Health Matters, 1999. 7(13): p. 11.
- 3. Asemota, O.A. and P. Klatsky, *Access to infertility care in the developing world: the family promotion gap.* Seminars in Reproductive Medicine, 2015. 33(1): p. 6.

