Randomization risk: You will be assigned to a treatment program by chance, and the treatment you receive may prove to be less effective or to have more side effects than the other study treatment(s) or other available treatments. Side effects risk: You may have side effects while on the study. Everyone taking part in the study will be watched carefully for any side effects. As with anyone undergoing fertility treatments, side effects may be mild or serious. Fertility treatment risks (either Group 1 or Group 2 participants): You will be receiving fertility medications to stimulate your ovaries to grow multiple eggs. Some of the more common side effects from this treatment include: bloating, cramping, nausea, headache, visual changes, hot flashes, and mood changes. You also have a small risk of more serious side effects or complications including ovarian hyperstimulation syndrome (OHSS), dehydration, lightheaded/dizziness, and abdominal discomfort. From the egg retrieval process, there are risk associated with anesthesia and procedural risks such as bleeding, infection and injury that your treatment physician will describe to you in more detail during the consenting process. Your ovaries will be stimulated using the minimal stimulation protocol. This is a lower cost stimulation and sometimes can produce a smaller quantity of eggs than full stimulation. Due to the smaller number of eggs, there may be a reduced pregnancy rate.	
INVOcell device risks (Group 1 participants):	

- There is a small risk that the placement and retention of the INVOcell device may be slightly uncomfortable for the patient, though studies have shown there has been no significant report of discomfort. During the device retention studies performed, 14/15 women reported no or mild discomfort.
- There is also a chance that the device may be expulsed from the vagina. This has never
 occurred with the device, and if it were to occur, you will have been trained on how to
 replace the device into the vagina.
- There is a small risk of failure of embryo development that may occur regardless of which study group you are in. This risk may be slightly increased with the INVOcell device.

Unknown Risks: The experimental treatments may have side effects that no one knows about yet. The researchers will let you know if they learn anything that might make you change your mind about participating in the study.

12.3

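### All three pregnancy outcomes are counted per embryo transferred or per transfer, so a randomized woman whose culture yields nothing to transfer drops out of them

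*Combined protocol and SAP*

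**What the plan says.** Section 7.13 places randomization late: "patients will not be randomized to either arm of the study (IVC versus IVF) until the day of trigger". Retrieval, fertilization, culture and transfer all follow it.

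Section 7.9 states what separates the arms: "The only difference between the two groups will be the culturing/growth of the embryos". Section 7.10 makes clear that fertilization is part of that step, describing use of the "INVOcell device instead of the standard in-vitro fertilization (IVF) for fertilization and growth of embryos".

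Section 7.25 defines the three pregnancy outcomes:

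- Item c, implantation (the primary outcome under section 7.3): "number gestational sacs seen on early pregnancy 6-week ultrasound divided by number of embryos transferred".
- Item d, clinical pregnancy: "number of fetal poles with heartbeat seen on ultrasound divided by the number of embryos transferred".
- Item e, live birth: "number of living babies delivered divided by the number of transfers".

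On culture failure, the device risks in section 12.2 say: "There is a small risk of failure of embryo development that may occur regardless of which study group you are in". They continue: "This risk may be slightly increased with the INVOcell device".

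The text defines no analysis population, makes no intention-to-treat statement, names no outcome per woman randomized, and has no rule for a randomized woman without a transfer. The allowance in section 9.1 to consent up to 50 women concerns recruitment and does not settle how such a woman is analyzed.

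**The concern.** The randomized intervention acts between randomization and transfer, and the denominators of items c to e begin at transfer. Comparing the arms on those rates compares only women who got through the step under study. If one culture method leaves more women with nothing to transfer, that loss appears in none of the three rates so long as success once transferred is the same.

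This matters more because the hypothesis in section 4.1 is that clinical pregnancy rates will be similar. Leaving out culture failures can make the arms look similar when they are not. Section 7.25 expects only 1 to 3 embryos per patient, so some women may have a single embryo whose arrest means no transfer.

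No test, margin or go/no-go rule rests on these rates. What is at stake is what the pilot hands to the larger trial it may lead to: how many women who start each culture method reach transfer, and how many become pregnant.

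**Working it through.** **No planned figure to reproduce.** The plan states no alpha, power, effect size or expected no-transfer rate. The structural point comes from the definitions; the sizes below rest on stated assumptions.

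**Step 1: contribution of a woman without a transfer.**

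| Outcome | Adds to numerator | Adds to denominator |
|---|---|---|
| Implantation (c) | 0 sacs | 0 embryos transferred |
| Clinical pregnancy (d) | 0 fetal poles | 0 embryos transferred |
| Live birth (e) | 0 babies | 0 transfers |

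She is absent from all three. She still counts in the fertilization rate if mature oocytes were retrieved.

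**Step 2: effect of one such woman.** Assume live birth per transfer is p in both arms, with at most one baby per transfer. With n women per arm, each extra device-arm woman without a transfer changes the per-randomized difference by −p/n, while the planned per-transfer difference stays 0. An extra woman in the IVF arm moves it equally the other way. Section 9.1 gives n = 16 and section 7.25 gives n = 20, so both are shown.

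| p (assumed) | n = 16 | n = 20 |
|---|---|---|
| 30% | 1.9 points | 1.5 points |
| 40% | 2.5 points | 2.0 points |
| 50% | 3.1 points | 2.5 points |

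**Step 3: expected loss under an arrest model.** Assume each of m embryos arrests independently, with probability a0 (IVF) or a1 (device). The chance of no transfer is a^m, and the hidden loss at p = 40% is 0.40 × (a1^m − a0^m).

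| Arrest, IVF v device (assumed) | m = 1 | m = 2 | m = 3 |
|---|---|---|---|
| 5% v 7.5% | 1.0 points | 0.13 | 0.01 |
| 10% v 15% | 2.0 points | 0.5 | 0.095 |
| 15% v 20% | 2.0 points | 0.7 | 0.19 |

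The loss is concentrated in women with one embryo.

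**Step 4: scale.** The standard error of a per-woman difference at 40% is √(2 × 0.4 × 0.6 / n) = 17.3 points for n = 16 and 15.5 points for n = 20. The pilot could describe a difference of the size in steps 2 and 3 but could not establish it.

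**The case against.** **Live birth is not fully blind.** Section 7.9 has all embryos transferred, so more arrest also means fewer embryos per transfer, and babies per transfer falls too. Assume 25% live birth per embryo, independent embryos, and arrest of 10% v 15%:

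- Two embryos: babies per transfer = 0.50/(1 + a) = 45.5% v 43.5%, a visible gap of 2.0 points. Babies per woman = 0.50 × (1 − a) = 45.0% v 42.5%, a gap of 2.5. About 0.5 points stay hidden.
- Three embryos: 3.6 of 3.75 points are visible, so about 0.15 stay hidden.

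This is right, and complete masking of live birth in such a model needs women with a single embryo. The hidden parts, however, are close to the 0.5 and 0.095 in step 3, and the two per-embryo outcomes, including the primary, remain blind throughout.

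**Direction is unsupported.** The only text suggesting excess loss with the device is the cautious risk wording in section 12.2. The cleavage figures cited in section 7.6 (93% IVF v 97% device) point the other way, and section 9.8 excludes some women at higher risk of no transfer, such as those with AFC below 8 or a prior cycle without fertilization. This stands: direction is unknown.

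**Early failure is already measured.** Fertilization rate uses all mature oocytes and is compared on day 3, and embryo quality is an outcome. This narrows the gap. Neither gives the number of women with nothing to transfer.

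**Implantation is conventionally per embryo, and this is a descriptive pilot.** Both are true. The planned rates need not be removed, and no error-rate or power problem is claimed.

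**Conclusion.** The concern holds. As written, section 7.25 conditions the primary outcome and both pregnancy secondaries on reaching transfer, an event after randomization that the device may affect, and no per-randomized rate stands beside them. The implantation rate itself is not wrong.

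The size and direction of any distortion cannot be derived from the documents. Under the assumptions shown, it is 1.5 to 3.1 points of live birth for each extra woman without a transfer. In expectation it is 1 to 2 points with one embryo, 0.1 to 0.7 with two and under 0.2 with three. These rest on assumed success and arrest rates, equal live birth per transfer and independent embryos. The effect may be small, and it lies well inside the pilot's sampling error. The change is still worth making because it is cheap and supplies a quantity that the larger trial would need.

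**What to change.** In section 7.25:

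1. Keep items c to e and label them as conditional on transfer.
2. Add clinical pregnancy and live birth as women with at least one event divided by women randomized, analyzed as randomized. Count a woman with no transfer from the study cycle as having no event.
3. State that the added rates change the numerator (women instead of fetal poles or babies) as well as the denominator.
4. Tabulate by arm the women without a transfer, with reasons. Put women with unknown outcome after a transfer in a separate row.
5. As a clarification only, state which transfers count toward items c to e. Section 7.9 has every embryo transferred on day 3, while section 7.14 allows freezing for later use; the two passages must be reconciled.

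The cost is plan wording and a few table rows, with no new data collection. The drawback is that the added rates are not directly comparable with published per-embryo or per-transfer figures. With at most one baby per transfer, live birth per woman is lower than per transfer whenever someone has no transfer. Clinical pregnancy per woman can be higher or lower than per embryo. At an assumed 33% per embryo and 10% of women without a transfer, it is 0.33 × 0.90 = 29.7% with one embryo and (1 − 0.67²) × 0.90 = 49.6% with two.

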8.0 Drugs and Devices

	Trugs and Devices	
8.	* DRUGS AND/OR BIOLOGICS: Are you STUDYING any drugs and/or biologics that are either approved or unapproved: (REQUIRED)	
t	Note: This question is frequently answered incorrectly. If any drugs or biologics, approved or unapproved, are being administered under this protocol, you should check 'Yes' unless you are absolutely sure that NONE of the drugs are part of the research protocol. Tip: Ask the PI or the sponsor if you are not sure how to answer this question.	
8.	* MEDICAL DEVICES: Are you STUDYING any medical devices, in vitro diagnostics, or assays that are either approved or unapproved:(REQUIRED)	
6	Yes O No	
8.4	* NSR: Are you requesting a Non-Significant Risk (NSR) determination for an investigational device: (REQUIRED) Note: an NSR determination is different from an Investigational Device Exemption (IDE). Check the Help link for more guidance on what types of devices can qualify for an NSR determination.	
(D Yes ⊙ No	

- 8.5 LIST THE DEVICES: List the medical devices or in vitro diagnostics to be studied or used. In the device details screen you will be asked questions such as:
 - Whether the device is FDA approved or investigational
 - Medicare device category
 - If the device will be provided at no cost

- If an IDE is necessary, the IDE number, and who holds the IDE
- Risk category of the device

9.1 ENROLLMENT TARGET: How many people will you enroll:

If there are multiple participant groups, indicate how many people will be

50

in each group:

• FDA status of the device

Please see the UCSF IRB website for more details about the use of devices in research, including the Investigator Checklist for Significant Risk, Non-Significant Risk, and/or IDE Exempt Device Studies

Verification of IDE numbers: If the sponsor's protocol does not list the IDE number, you must submit documentation from the sponsor or FDA identifying the IDE number for this study. Attach this documentation in the Other Study Documents section of the Initial Review Submission Packet.

If you have any correspondence from the FDA or sponsor regarding this device, please attach it to the application.

	IDE Numbe
Manufacturer/Supplier of Device Medicare Category Where will the Devices Be Stored Will Devices be supplied at no Cost Is this a HUD (HDE) HDE Number Is the Device FDA Approved Is this a new device or a new use of an already approved device INVO Bioscience In Clinic No No No No No No No No No N	

9.5 * STUDY POPULATIONS: Data will be collected from or about the following types of per that apply): (REQUIRED)	ople (check all
☐ Inpatients ☐ Outpatients ☐ Family members or caregivers ☐ Providers ☐ People who have a condition but who are not being seen as patients ☐ Healthy volunteers ☐ Students ☐ Staff of UCSF or affiliated institutions ☐ None of the above	
9.6 * SPECIAL SUBJECT GROUPS: Check the populations that may be enrolled: (REQUIRED)
 Children / Minors Subjects unable to consent for themselves Subjects unable to consent for themselves (emergency setting) Subjects with diminished capacity to consent ✓ Subjects unable to read, speak or understand English Pregnant women Fetuses Neonates Prisoners Economically or educationally disadvantaged persons None of the above 	
If not already addressed in the Background and Significance questions in the Research Plan section or elsewhere, explain why it is appropriate to include the types of subjects checked above in this particular study:	

Given our patient population, women who have a diagnosis of infertility or couples requiring donor sperm, there may be some individuals from different backgrounds and those that do not speak English. For those participants, we will be providing an interpreter for their native language, in addition to study documents printed in their native language.

Describe the additional safeguards that have been included in the study to protect the rights and welfare of these subjects and minimize coercion or undue influence:

Here are some examples:

- evaluating capacity to consent for individuals who may be decisionally impaired (specify how)
- calibrating payment amounts to be non-coercive for the financially disadvantaged
- conducting more in-depth evaluations of subjects' understanding of the study and the voluntary nature of participation
- involving advocates in the consent process

More information and other safeguards are described here: **Vulnerable Subject Populations** and **Recruiting Staff and Students**.

9.7 INCLUSION CRITERIA: Briefly describe the population(s) that will be involved in this study. Include anyone that data will be collected from or about (e.g. patients, healthy controls, caregivers, providers, administrators, students, parents, family members, etc.):

Inclusion Criteria:

- -Normal uterine cavity
- -One or more years of infertility
- -Normal male partner (or donor) semen analysis

9.8 EXCLUSION CRITERIA: List any exclusion criteria (e.g. reasons why someone would not be included in the study):

Exclusion Criteria:

- -Age < 18 or > 37 years old
- -AFC < 8
- -Abnormal male partner (or donor) semen analysis
- -Vaginal inflammation or genital (vaginal, uterine, tubal) infection -Uncontrolled chronic disease (such as uncontrolled diabetes or hypertension)
- -Uterine anatomic abnormalities
- -Allergy to plastics or inability to use diaphragm retention device
- -Untreated hydrosalpinx
- -Drug of alcohol abuse (defined by >14 drinks/week)
- -Prior history of IVF cycle where fertilization did not occur
- -History of recurrent pregnancy loss

9.9 * RESEARCH CONDUCTED ON PATIENT CARE WARDS: Do any study activities take place on patient care units at UCSF medical facilities: (REQUIRED)

C Yes C No

10.0 **Recruitment and Consent** 10.1 * RECRUITMENT METHODS: What kinds of methods will be used to identify potential participants for recruitment (check all that apply): (REQUIRED) ▼ Medical records review Recruitment registry Re-contact of participants from the investigators' previous studies Referrals from colleagues (attach the 'Dear Colleague' letter or other recruitment materials you will provide to colleagues) Referrals from the community / word of mouth Advertisements (flyers, brochures, radio or t.v. ads, posting on clinical research sites or social media, presentation of the study at community events/media, etc.) Online recruiting tool such as TrialSpark CTSI Recruitment Services unit Other method (describe below) Attach your recruitment materials (e.g., flyers, ads, recruitment letter templates, email text, etc.) in the Other Study Documents section of the Initial Review Submission Packet Form. * Provide details about the other recruitment methods: (REQUIRED) Participants will be recruited from the Center for Reproductive Health at the University of California at San Francisco. All eligible women will be identified by the clinician at the time of their initial infertility evaluation and approached about the study. 10.2 * SEARCHING OF MEDICAL RECORDS: (REQUIRED) Whose patients are they: ✓ Investigators' own patients or patients seen within the same practice Patients not under the care of the investigators How and by whom will records be accessed and searched (check all that apply): Self-search in APeX or other medical records source Self-search using UCSF's Research Cohort Selection Tool CTSI Consultation Service Recruitment Services UCSF Academic Research Services (ARS) University of California Research Exchange (UC ReX) ✓ Other method (describe below) Describe the other ways medical records may be accessed and searched to identify prospective participants: The IDEAS electronic medical record system used by the Center for Reproductive Health will also be used. 10.3 DETERMINATION OF ELIGIBILITY: How, when, and by whom will eligibility for recruitment be determined: Inclusion Criteria: -Normal uterine cavity -One or more years of infertility -Normal male partner (or donor) semen analysis Exclusion Criteria:

-AFC < 8 -Abnormal male partner (or donor) semen analysis -Vaginal inflammation or genital (vaginal, uterine, tubal) infection -Uncontrolled chronic disease (such as uncontrolled diabetes or hypertension) -Uterine anatomic abnormalities -Allergy to plastics or inability to use diaphragm retention device -Untreated hydrosalpinx -Drug of alcohol abuse (defined by >14 drinks/week) -Prior history of IVF cycle where fertilization did not occur -History of recurrent pregnancy loss	
10.4 * INITIATION OF CONTACT: Who initiates contact (check all that apply): (REQUIRED)	
 ✓ Investigators/study team ☐ UCSF recruitment unit (e.g. CTSI Consultation Services) ✓ Potential participant ☐ Other (explain below) 	
10.5 * HOW IS CONTACT INITIATED: (check all that apply): (REQUIRED)	
✓ In person Phone Letter / email Website or app ✓ Other (explain below)	
 10.6 RECRUITMENT PLAN: Based on the checkboxes you chose above, please provide a nai describing your recruitment plan. We want to know: Who is conducting the search for potential participants, and how? How are potential subjects being approached for recruitment? By whom, and was if there will be more than one participant group (e.g. patients, healthy controls, care, members, providers, etc.), provide details about the recruitment plans for each group 	hen?
(Recommended length - 100-250 words)	
Participants will be recruited from the Center for Reproductive Health at the University of California at San Francisco. All eligible women will be identified by the clinician at the time of their initial infertility evaluation and approached about the study. Women who are interested in participating will receive consent forms to review. They will then be approached by the research team for further information regarding the study. At that time, informed consent will be performed by the research team. The enrollment target is 40 patients with 20 patients randomized to each group: intravaginal culture with INVOcell device versus in-vitro fertiilzation and culture of embryos. We expect enrollment to take at least 6 months given the inclusion and exclusion criteria for this study.	
Participants will be recruited from the Center for Reproductive Health at the University of California at San Francisco. All eligible women will be identified by the clinician at the time of their initial infertility evaluation and approached about the study. Women who are interested in participating will receive consent forms to review. They will then be approached by the research team for further information regarding the study. At that time, informed consent will be performed by the research team. The enrollment target is 40 patients with 20 patients randomized to each group: intravaginal culture with INVOcell device versus in-vitro fertiilzation and culture of embryos. We expect	obtained from senting each,

 Not be able to provide consent and will have a family member consent for them, as in the case of a critically ill or unconscious patient (surrogate consent) Not be able to provide consent (emergency waiver of consent - allowed for minimal risk research or greater than minimal risk research with an approved community consultation plan) Not know about the study, as in the case of chart reviews or observations of public behavior (waiver of consent) Other method (describe below) Attach your consent form, information sheet, or electronic consent text in the Informed Consent Documents section of the Initial Review Submission Packet Form. 	
 * CONSENT PROCESS: Describe the process for obtaining informed consent, including who will have the consent discussion and when participants will be asked to sign the crelation to finding out about the study: (REQUIRED) We encourage researchers to guidance on obtaining and documenting informed consent. If there are multiple groups being consented differently, provide details about the process for each group. If you are relying on verbal or implied consent, provide details about how that we for studies using online recruitment and consent or consent via mail, provide details. 	consent form in oreview our he consent will happen.
At their first visit to the Center for Reproductive Health at the University of California at San Francisco, all eligible women will be identified by the clinician at the time of their initial infertility evaluation and approached about the study. At this time they can indicate participation or decline participation. They may consent at this visit or they will be given materials to take home and consider (patient information sheet and consent form). If they have not done so already, when patients are ready to start their stimulation cycle, they will confirm whether or not they wish to participate in the study and sign the consent forms. A study-specific research assistant or healthcare affiliate involved in the care of the patient will obtain informed consent at the first or second clinical visit. Or, if the prospective subject wishes, she may return at a later time to consent to study participation as long as this all occurs prior to oocyte retrieval day.	
* It is important that the people obtaining consent are qualified to do so. Briefly describe the training and experience these individuals have in obtaining informed consent: (REQUIRED) All people obtaining informed consent are medical affiliates who have years of experience in the field of obstetrics and gynecology in addition to obtaining consent with other IRB-approved studies. In addition, they have taken required courses through the CHR regarding protection of human subjects.	
* CONSENT COMPREHENSION: Indicate how the study team will assess and enhance the understanding of study procedures, risks, and benefits prior to signing the consent for that apply): (REQUIRED) Tip: Review the Consent Comprehension - Learning Note bubble at the right for specific questions that can be asked to assess comprehension, of the UCSF Decision-Making Capacity Assessment Tool, and review our guidance on obtain verbal informed consent for more detail on how to conduct the assessment.	m (check all es in the Help consider using
 □ The study team will engage the potential participant in a dialogue, using open-ended questions about the nature of the study or the experimental treatment, the risks and benefits of participating, and the voluntary nature of participation □ Potential participants will be asked or shown a series of questions to assess their understanding of the study purpose, procedures, risks and benefits, as well as the voluntary nature of participation (especially appropriate when the consent process happens online or through a mobile health app) ☑ Other method (describe below): 	

method to assess comprehension:	
The consenting research assistant or investigator will be responsible for determining whether subjects understand the consent process. If a participant asks questions that the research assistant (or other healthcare affiliate obtaining consent) cannot answer, the question will be directed to research supervisor or Principal Investigator.	
* NON-ENGLISH CONSENT METHOD: Indicate which method(s) you will use to consenglish speaking subjects: (REQUIRED)	ent non-
 ✓ Preferred Method—Consent form and other study documents will be available in the subject's primary language Personnel able to discuss participation in the patient's language will be present for the consent process. ✓ Short-Form—A qualified interpreter will translate the consent form verbally, and subjects will be given the Experimental Subject's Bill of Rights in their primary language, following instructions in Those Who do not Read, Speak or Understand English for required witnessing 	
* Explain how you will maintain the ability to communicate with non-English speakers throughout their participation in the study: (REQUIRED)	
Non-English speakers, as always, will be provided with an interpreter of their native language. In addition, they will receive study documents in their native language for review.	
10.13 TIME: What is the estimated time commitment for participants (per visit and in total):
The study will not require the patient to devote any additional time beyond what their time commitment is for the standard IVF treatment.	
IMPORTANT TIP: Ensure this information is consistent with the information provided in the consent form.	
10.14 ALTERNATIVES: Is there a standard of care (SOC) or usual care that would be offered to prospective participants at UCSF (or the study site) if they did not participate in the study:	
⊙ Yes ○ No	
Describe the care that patients would ordinarily receive at the medical center if they did not participate in this study (provide details, assuming that some of the IRB members are not specialists in this field):	
The patients included in the study would be either randomized to the standard, in-vitro fertilization (IVF) technique of embryo culture, versus the newer intra-vaginal culture (IVC) technique. If a patient decides not to participate in the study, they will receive the standard IVF treatment.	
10.15 OFF-STUDY TREATMENT: Is the study drug or treatment available off-study:	
○ Yes⊙ No○ Not applicable	

Waiver of Consent/Authorization for Recruitment Purposes This section is required when medical records may be reviewed to determine eligibility for recruitment.

11.1 * PRACTICABILITY OF OBTAINING CONSENT PRIOR TO ACCESS: Study personnel need to access protected health information (PHI) during the recruitment process and it is not practicable to obtain informed consent until potential subjects have been identified: (REQUIRED)			
⊙ Yes			
If no , a waiver of consent/authorization is NOT needed.			
11.2 * RISK TO PRIVACY: A waiver for screening of health records to identify potential sumore than minimal risk to privacy for participants:	ıbjects poses no		
Yes			
If no , a waiver of authorization can NOT be granted.			
i iie, a waiver of dathorization can not be granted.			
11.3 * RIGHTS/WELFARE: Screening health records prior to obtaining consent will not adsubjects' rights and welfare:	versely affect		
• Yes			
If no , a waiver of authorization can NOT be granted.			
11.4 * IDENTIFIERS: Check all the identifiers that will be collected prior to obtaining info	med consent:		
▼ Names			
✓ Dates			
✓ Postal addresses			
▼ Phone numbers			
▼ Fax numbers			
✓ Email addresses			
☐ Social Security Numbers*			
✓ Medical record numbers			
Health plan numbers			
Account numbers			
✓ License or certificate numbers			
☐ Vehicle ID numbers			
✓ Device identifiers or serial numbers			
✓ Web URLs ✓ IP address numbers			
✓ IP address numbers ✓ Biometric identifiers			
✓ Facial photos or other identifiable images			
Any other unique identifier			
None			
Note: HIPAA rules require that you collect the minimum necessary.			
11.5 * HEALTH INFORMATION: Describe any health information that will be collected prio informed consent:	r to obtaining		
